12.5. Level of Significance

All confidence intervals will be 95% and tests will be performed at two sided 0.05% level. Since this is an exploratory study, no multiplicity adjustment will be performed.

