12.2. Statistical Analyses

12.2.1. Primary Analyses

Co-Primary Endpoints:

- Correlation of % change in spleen volume at Week 24 compared to baseline versus final titrated dose.
- Correlation of % change in Total Symptom Score as measured by the modified MFSAF v2.0 diary at Week 24 compared to baseline versus final titrated dose.

The null hypothesis is that the correlation between percent change in spleen volume or total symptom score and final titrated dose is zero. The test will be based on the t test for a product-moment correlation coefficient:

$$t = r_{xy} \sqrt{(n - 2) / (1 - r_{xy}^2)}$$

(Cohen 1988, Formula 3.1.1)

A two-sided alpha of 5% will be used. With a sample size of 150, the critical correlation that is needed to reject H_0 is 0.16. If the absolute value of the observed correlation is 0.16 or higher, H_0 will be rejected. In order to keep the overall alpha at 5%, a sequential testing procedure will be used: First we will test the correlation with % change in spleen volume, and only if the null hypothesis of no correlation can be rejected will we continue to test the correlation with % change in Total Symptom Score.

Safety Endpoints:

Safety and tolerability will be assessed by monitoring the frequency, duration and severity of adverse events, performing physical examinations, collecting vital signs, collecting laboratory data for hematology, serum chemistry, coagulation parameters, and lipid panel through Week 156.

Change in platelet count from baseline to each visit where the variables are measured will be tabulated with summary statistics.

Proportion of subjects with new onset of Grade 4 thrombocytopenia events, and proportion of subjects with new onset of Grade 2 or higher hemorrhage, as measured by CTCAE will be tabulated with summary statistics. The hazard functions of time to onset of the above two safety measures will be estimated using life table method.

Adverse events will be tabulated by the Medical Dictionary for Regulatory Activities (MedDRA[®]) preferred term and by system organ class. Severity of AEs will be based on the CTCAE scale as indicated in [Section 11.1.1](#).

The subset of AEs that are considered by the Investigator to be related to study drug will be considered to be treatment-related AEs. If the Investigator does not specify the relationship of the AE to study drug, the AE will be considered to be treatment-related. The incidence of AEs and treatment-related AEs will be tabulated.

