### 4.3. Sample Size Considerations

Approximately 150 subjects will be enrolled in order to assess (on the efficacy side) the dose-effect correlation (between percent changes from baseline in spleen volume/total symptom score at Week 24 and final titrated dose level). Using an alpha of 5% (2-sided), this sample size gives a power of 96% to reject the null hypothesis of no dose-effect correlation if the true correlation is 0.30. The power is 87% if the true correlation is 0.25, and the power is 69% if the true correlation is 0.20. These calculations are based on [Cohen 1988](#), Formula 12.3.4. SAS procedure POWER is used and the power curves are displayed in Figure 1.

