#### **5.4.2. Control of Type I Error**

All confidence intervals will be 95% and tests will be performed at 2-sided 0.05% level. Because of the exploratory nature of the study analyses, except for tests regarding the coprimary endpoints, no multiplicity adjustment will be performed. To control overall Type I error in testing hypotheses regarding the coprimary endpoints, a sequential testing procedure will be used.

- Step 1 will test the correlation between percent change from baseline in spleen volume at Week 24 and the last titrated dose level, and only if the null hypothesis of no correlation can be rejected, Step 2 will be carried out.
- Step 2 will test the correlation between percent change from baseline in total symptom score at Week 24 and the last titrated dose level. In case Step 1 fails to reject the null hypothesis, the inferential comparison (p-values) of Step 2 will still be generated for descriptive purposes only.

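### Protocol 12.5 and SAP 5.4.2 set tests at 0.05% two-sided, 100 times stricter than the 5% behind the critical value and power, and Protocol 12.5 also rules out the multiplicity control that 12.2.1 requires

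*Protocol*

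**What the plan says.** **Level of the tests**
- Protocol 12.5, Level of Significance: "tests will be performed at two sided 0.05% level. Since this is an exploratory study, no multiplicity adjustment will be performed". The level stands in the same sentence as 95% confidence intervals.
- SAP 5.4.2, Control of Type I Error: "All confidence intervals will be 95% and tests will be performed at 2-sided 0.05% level".
- Protocol 12.2.1, Primary Analyses: "A two-sided alpha of 5% will be used". It continues "With a sample size of 150, the critical correlation that is needed to reject H_0 is 0.16", and says that an observed absolute correlation at or above that value rejects.
- Protocol 12.4 and SAP 4.3 base the power on two-sided 5%. The SAP's words are "Using an alpha of 5% (2-sided), this sample size gives a power of 96" percent, for a true correlation of 0.30. Both then give 87% for 0.25 and 69% for 0.20.

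**Multiplicity**
- Protocol 12.2.1: "In order to keep the overall alpha at 5%, a sequential testing procedure will be used". Spleen volume is tested first, and Total Symptom Score only if the first null is rejected.
- Protocol 12.5: no multiplicity adjustment, on the ground that the study is exploratory. No exception is given.
- SAP 5.4.2: no adjustment except for the co-primary tests. It then sets out the two-step sequence. If Step 1 fails, the Step 2 p-value is descriptive only.

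**The concern.** The two sections whose purpose is to fix the test level give a figure 100 times smaller than the one used to design the study (0.05 / 0.0005 = 100). The figure appears in both documents.

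The SAP does not settle the matter. Section 7.1 gives the t statistic and the SAS code but no alpha, and Section 3.2 gives the hypotheses but no alpha. The 5% in Section 4.3 is a sample-size assumption. The one SAP sentence saying at what level tests will be performed is the 0.05% one, and it stands in the section that defines the sequential gate. The 0.16 cut-off is in the protocol only.

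At stake is the decision threshold for the first co-primary endpoint and, through the gate, the standing of the second. If the observed correlation lands between the two thresholds, choosing the lenient reading after seeing the data would look post hoc.

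Separately, a reader of Protocol 12.5 alone would conclude that both co-primary tests may be run at full level with no ordering, which is what 12.2.1 forbids.

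**Working it through.** **Inputs.** n = 150 (Protocol 12.4, SAP 4.3), taken as 150 paired observations, as the documents do. True correlations 0.30, 0.25 and 0.20 (same sections). Two-sided alpha 0.05 (Protocol 12.2.1 and 12.4, SAP 4.3) or 0.0005 (Protocol 12.5, SAP 5.4.2).

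**Formulas.**
- Critical correlation, from the t test in Protocol 12.2.1 solved for r: r_c = t / √(n − 2 + t²), with t the upper alpha/2 point on 148 degrees of freedom.
- Power by Fisher's z: Φ( √(n − 3) × [atanh(ρ) + ρ/(2(n − 1)) − atanh(r_c)] ), with √147 = 12.124.

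**Step 1: reproduce the plan's figures at 5%.**
- t = 1.976, so r_c = 1.976 / √(148 + 3.905) = 0.1603. The plan says 0.16.
- atanh(0.1603) = 0.1617.
- ρ = 0.30: 12.124 × (0.3105 − 0.1617) = 1.804, power 96.4%.
- ρ = 0.25: 12.124 × (0.2563 − 0.1617) = 1.146, power 87.4%.
- ρ = 0.20: 12.124 × (0.2034 − 0.1617) = 0.505, power 69.3%.

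These match the stated 96%, 87% and 69%. A simulation of 40,000 trials per value gave 96.3%, 87.4% and 69.1%. One-sided 5% would give 98%, 93% and 79%, so the design level is two-sided 5%.

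**Step 2: the same at the literal 0.05%.**
- t = 3.559, so r_c = 3.559 / √(148 + 12.670) = 0.2808, and atanh(0.2808) = 0.2886.
- ρ = 0.30: 12.124 × (0.3105 − 0.2886) = 0.266, power 60.5%.
- ρ = 0.25: 12.124 × (0.2563 − 0.2886) = −0.392, power 34.8%.
- ρ = 0.20: 12.124 × (0.2034 − 0.2886) = −1.032, power 15.1%.

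Simulation gave 60.6%, 35.4% and 15.0%.

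| | Two-sided 5% | Two-sided 0.05% |
|---|---|---|
| Critical \|r\| | 0.160 | 0.281 |
| Power, ρ = 0.30 | 96% | 60% |
| Power, ρ = 0.25 | 87% | 35% |
| Power, ρ = 0.20 | 69% | 15% |

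Keeping the stated power at 0.05% would need about 289, 329 and 389 subjects respectively.

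**Step 3: what the gap means for a result.** The disputed band runs from 0.160 to 0.281 and contains two of the three correlations used for the power statement. Take an observed r = 0.20: t = 0.20 × √(148 / 0.96) = 2.48 and p = 0.014. The Fisher 95% interval is tanh(0.2027 ± 1.96/12.124), about 0.04 to 0.35. Table shell 14.2.1.1 prints the p-value and this interval together, so the interval would exclude zero while the test at 0.05% did not reject.

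**Step 4: multiplicity.** If the sequence were dropped and each co-primary null tested at 5%, the chance of at least one false rejection with independent tests would be 1 − 0.95² = 9.75%, against the 5% overall level that 12.2.1 promises.

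**The case against.** The best defence is that 0.05% is a plain slip. The same sentence pairs it with 95% intervals, which correspond to 5% tests, and every design figure reproduces at 5%. Protocol 12.2.1 is the specific rule for the co-primary endpoints: it names the alpha, the cut-off and the rejection rule, and a specific rule would normally prevail over a general sentence such as 12.5. SAP 4.3 also ties 5% to the same null hypothesis and refers to Section 5.4.2. On this view the 60%, 35% and 15% are hypothetical, since nobody would run the tests at 0.0005. On multiplicity, a fixed sequence spends the full alpha on each test, so 12.5 may be meant for the other analyses only. The study is single-arm and described as exploratory.

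Much of this stands. The intention is clear, no calculated quantity is wrong, and the reduced power applies only if the literal level is used. The multiplicity conflict is confined to the protocol.

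It does not remove the conflict. Neither document says which section prevails. The SAP repeats neither the 5% decision level nor the 0.16 rule, and its error-control section gives the stricter figure. Protocol 12.5 does not limit its no-adjustment statement to other analyses.

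**Conclusion.** Wrong as written, and to be corrected before the co-primary analysis. Protocol 12.5 and SAP 5.4.2 state a level that cannot hold together with Protocol 12.2.1, Protocol 12.4 and SAP 4.3. At n = 150 the two readings put the critical |r| at 0.160 and 0.281. The stated power exists only at 5%. The sample size is sound once the level is stated as two-sided 5%.

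Protocol 12.5 also contradicts 12.2.1 on multiplicity, where SAP 5.4.2 is correct.

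The figures assume 150 complete pairs and, for power, bivariate normality. With fewer pairs both critical values rise, but the contradiction is the same.

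**What to change.** - Protocol 12.5 and SAP 5.4.2: replace 0.05% with two-sided 5% (alpha = 0.05).
- Protocol 12.5: say that no multiplicity adjustment is made except for the fixed-sequence test of the two co-primary endpoints in 12.2.1, as SAP 5.4.2 already does.

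The cost is a wording correction in each document. The sample size, critical value, power, trial conduct and data collection do not change.

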13. STUDY DRUG MATERIALS AND MANAGEMENT

13.1. Investigational Product Description

Ruxolitinib Phosphate tablets will be provided as 5 mg tablets packaged as 60 count in high-density polyethylene bottles.

13.1.1. Study Drug Packaging, Labeling and Preparation

All bottles of Incyte investigational product contain the following language: “Caution: New Drug—Limited by Federal law to investigational use.”

13.1.2. Study Drug Storage and Stability

Ruxolitinib Phosphate 5 mg tablets are packaged as 60-count in high-density polyethylene (HDPE) bottles. The bottles of tablets should be stored at room temperature, 15°C to 30°C (59°F to 86°F). Stability studies will be conducted on clinical batches to support the clinical trial.

13.2. Study Drug Accountability, Handling, and Disposal

Responsibility for drug accountability at the study site rests with the Investigator; however, the Investigator may assign some of the drug accountability duties to an appropriate pharmacist or designee. Inventory and accountability records must be maintained and readily available for inspection by the study monitor and are open to inspection at any time by any applicable regulatory authorities.

The Investigator or designee will be expected to collect and retain all used, unused, and partially used containers of study medication until the end of the study. The Investigator or designee must maintain records that document:

- investigational product delivery to the study site
- the inventory at the site
- use by each subject including pill/unit counts from each supply dispensed
- return to the Investigator or designee.

These records should include dates, quantities, batch/serial numbers (if available), and the unique code numbers (if available) assigned to the investigational product and study subjects.

The investigational product must be used only in accordance with the protocol. The Investigator will also maintain records adequately documenting that the subjects were provided the correct study medication specified.

Completed accountability records will be archived by the site. At the completion of the study, the Investigator or designee will oversee shipment of any remaining study drug back to the Sponsor or Sponsor’s designee for destruction according to institutional standard operating procedures. If local procedures mandate site destruction of investigational supply, prior written approval must be obtained from Incyte.

14. STUDY ADMINISTRATION

14.1. Data Management

14.1.1. Data Collection

The Investigator will be provided with an eCRF for each subject. Entries made in the eCRF must be verifiable against source documents, or, in certain circumstances, as directed by the Sponsor, have been directly entered into the eCRF, in which case the entry in the eCRF will be considered as the source data. Data reported in the eCRF that are derived from source documents should be consistent with the source documents or the discrepancies should be explained. The Investigator will be responsible for reviewing all data and eCRF entries and will sign and date the designated pages in each subject's eCRF, verifying that the information is true and correct. Queries generated by Data Management will be sent to the study site for resolution. The Investigator is responsible for the review and approval of all responses.

14.1.2. Data Management

Data management will be performed from electronic case report forms (eCRFs). All eCRF data will be entered into a validated database. Laboratory data will be imported to the database electronically. All data entry, verification and validation will be performed in accordance with the current standard operating procedures of the Data Management Department at Incyte or its designee. The database will be authorized for lock once no data queries are outstanding, all study data are considered clean, and all defined procedures completed.

14.2. Study Monitoring

Qualified representatives of the Sponsor or Sponsor designees, "study monitors," will monitor the study according to a predetermined monitoring plan. Monitoring visits provide the Sponsor with the opportunity to:

- Evaluate the progress of the study.
- Verify the accuracy and completeness of CRFs.
- Assure that all protocol requirements, applicable laws and/or regulations, and Investigator's obligations are being fulfilled.
- Resolve any inconsistencies in the study records.

The Investigator must allow the study monitors to periodically review, at mutually convenient times, during the study and after the study has been completed, all CRFs and office, hospital, and laboratory records supporting the participation of each subject in the study. The CRFs and other documentation supporting the study must be kept up-to-date by the Investigator and the research staff at the investigative site. These study materials must be available for review by the study monitor, and/or other qualified representatives of the Sponsor, at each monitoring visit.

The study monitor will review the various records of the study (CRFs, subject medical and laboratory records, and other pertinent data). The study monitor will verify the CRF data against original source documentation for accuracy and completeness. The study monitor will identify

data discrepancies and collaborate with the Investigator and research staff to resolve the discrepancies in a timely manner. Protocol deviations will also be identified and recorded on a “Protocol Deviation Log.” The study monitor will follow an “Issue Escalation” plan in order to ensure that each issue identified during a monitoring visit is appropriately documented, reported, and resolved in a timely manner in accordance with the plan’s requirements.

14.3. Protocol Adherence

The Principal Investigator must obtain IRB approval for the investigation. Initial IRB approval, and all materials approved by the IRB for this study including the subject informed consent form and recruitment materials must be maintained by the Investigator and made available for inspection.

Each Investigator must adhere to the protocol as described in this document and agree that changes to the protocol, with the exception of medical emergencies, must be discussed and approved, firstly, by the Sponsor and, secondly, by the IRB/EC. Each Investigator is responsible for enrolling subjects who have met the protocol inclusion and exclusion criteria. The IRB/EC that granted original approval, or the IRB/EC currently responsible for overseeing the conduct of the study must be notified of all changes in and deviations from the protocol that may increase risk to the subject, and/or that may adversely affect the rights of the subject or validity of the investigation. The Investigator must send a copy of the approval letter from the IRB/EC to the Sponsor or CRO and retain the original in the site study regulatory file.

Major eligibility deviations must be reported to the IRB/EC in accordance with the IRB/EC requirements. During the course of the study, the monitor must notify the Sponsor of subjects found not to have met eligibility criteria. The medical monitor, in collaboration with the Investigator, will determine if the subject should be withdrawn from the study.

14.4. Financial Disclosure

All clinical investigators participating in clinical studies subject to FDA Regulation Title 21 Code of Federal Regulations (CFR) Part 54 – Financial Disclosure by Clinical Investigators, are required prior to study initiation to submit a completed Clinical Investigator Financial Disclosure Request Form that sufficiently details any financial interests and arrangements that apply. For the purpose of this regulation, clinical investigator is defined as any investigator or subinvestigator who is directly involved in the treatment or evaluation of research subjects, including the spouse and each dependent child of the clinical investigator. These requirements apply to both US and foreign clinical investigators conducting covered clinical studies.

Any new investigators or sub-investigators added to the covered clinical study during its conduct must also submit a completed Clinical Investigator Financial Disclosure Request Form. During a covered clinical study, any changes to the financial information previously reported by a clinical investigator must be reported to the Sponsor/designee. At the conclusion of the covered clinical study, the clinical investigators will be reminded of their obligation to report to the Sponsor/designee any changes to the financial information previously reported. The clinical investigators will also be reminded that they must report any changes in their financial information for a period of 1 year after completion of the covered clinical study.

15. QUALITY CONTROL AND QUALITY ASSURANCE

15.1. Sponsor Audits

At some point during the study, individuals from the Sponsor's Quality Assurance department and/or their authorized representative may visit the Investigator's site to conduct an audit of the study. The purpose of this visit will be to determine the Investigator's adherence to the protocol, applicable regulations, and the Sponsor's procedures, in addition to assessing the accuracy of the study data. Prior to initiating this audit, the Investigator will be contacted by the Sponsor to arrange a convenient time for this visit. The Investigator and staff are expected to cooperate with the auditors and allow access to all subject records supporting the CRFs and other study-related documents.

15.2. Inspection by Regulatory Authorities

At some point during the investigational product's development program, a regulatory authority may visit the Investigator to conduct an inspection of the study and the site. The Investigator and staff are expected to cooperate with the inspectors and allow access to all source documents supporting the CRFs and other study related documents. The Investigator must immediately notify the Sponsor when contacted by any regulatory authority for purposes of conducting an inspection.

16. ETHICS

16.1. Ethical Conduct of the Study

This study will be performed in accordance with ethical principles that have their origin in the Declaration of Helsinki and conducted in adherence to the study protocol, Good Clinical Practices as defined in Title 21 of the US Code of Federal Regulations Parts 50, 54 56, 312 and Part 11 as well as ICH GCP consolidated guidelines (E6) and applicable regulatory requirements.

16.2. Written Informed Consent

An informed consent form (ICF) that includes both information about the study and the consent form will be prepared and given to the subject. This document will contain all the elements required by the ICH E6 Guideline for Good Clinical Practice and any additional elements required by local regulations. The document must be in a language understandable to the subject and must specify who informed the subject. Where required by local law, the person who informs the subject must be a physician.

The Principal Investigator(s) at each center will ensure that the subject is given full and adequate verbal and written information about the nature, purpose, and the possible risk and benefit of the study. Subjects must also be notified that they are free to discontinue study medication and withdraw from the study at any time. The subject should be given the opportunity to ask questions and allowed time to consider the information provided.

The subject's signed and dated ICF must be obtained before conducting any study procedures. The Principal Investigator(s) must maintain the original, signed ICF. A copy of the signed ICF must be given to the subject.

Preparation of the consent form is the responsibility of the Investigator and must include all elements required by the ICH GCP, and applicable regulatory requirements, and must adhere to the ethical principles that have their origin in the Declaration of Helsinki.

A template will be provided by Incyte. Incyte or its designee must review and approve all changes to site-specific ICFs.

The consent form must include a statement that the Sponsor or designee and regulatory authorities have direct access to subject records. Prior to the beginning of the study, the IRBs and/or IECs must provide the Investigator with written approval/favorable opinion of the written ICF and any other information to be provided to the subjects.

The Investigator will not undertake any measures specifically required for the clinical study until valid consent has been obtained.

The Investigator should inform the subject's primary physician about the subject's participation in the study if the subject has a primary physician and if the subject agrees to the primary physician being informed.

